REPRISE III: REpositionable Percutaneous Replacement of Stenotic Aortic Valve through Implantation of Lotus™ Valve System – Randomized Clinical Evaluation	
	the LOTUS Edge Valve, up to 20 subjects will be enrolled in the LOTUS Edge 29 mm Valve roll-in phase (29 mm valve only; a minimum of 2 roll-in subjects per center) before enrolling in the LOTUS Edge 29 mm Nested Registry.
Primary Endpoints	
Primary Safety Endpoint: Composite of all-cause mortality, stroke, life-threatening and major bleeding events, stage 2 or 3 acute kidney injury, or major vascular complications at 30 days
 
Primary Effectiveness Endpoint: Composite of all-cause mortality, disabling stroke, or moderate or greater paravalvular aortic regurgitation (based on core lab assessment) at 1 year
 
Powered statistical analyses for the primary safety endpoint and the primary effectiveness endpoint will be carried out on the randomized cohort.

Secondary Endpoint	
Moderate or greater paravalvular aortic regurgitation (based on core lab assessment) at 1 year
 
Powered statistical analysis for the secondary endpoint will be carried out on the randomized cohort.

Additional Measurements	
Additional measurements based on the VARCa,b endpoints and definitions (see Note 1 below) will be collected peri- and post-procedure, at discharge or 7 days post-procedure (whichever comes first), 30 days, 6 months, and 1, 2, 3, 4, and 5 years post index procedure, unless otherwise specified below.
 
 
• Safety endpoints adjudicated by an independent Clinical Events Committee (CEC): 
 
○ Mortality: all-cause, cardiovascular, and non-cardiovascular
 
○ Stroke: disabling and non-disabling
 
○ Myocardial infarction (MI): periprocedural (≤72 hours post index procedure) and spontaneous (>72 hours post index procedure)
 
○ Bleeding: life-threatening (or disabling) and major
 
○ Acute kidney injury (≤7 days post index procedure): based on the AKIN System Stage 3 (including renal replacement therapy) or Stage 2
 
○ Major vascular complication
 
○ Repeat procedure for valve-related dysfunction (surgical or interventional therapy)
 
○ Hospitalization for valve-related symptoms or worsening congestive
 
 
 

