#### **11.7.1. Medtronic CoreValve (Control) Cohort**

The IFU associated with the control device (CoreValve) should be followed. A final post-deployment aortogram of the ascending aorta must be performed and forwarded to the Core Laboratory with the procedural cine-angiogram for analysis.

Labels from devices used during the procedure (e.g., CoreValve, Introducer, etc.) should be retained so that they can be included in the appropriate source documents and reported in the eCRFs. During the procedure, designated center study personnel must capture necessary information on acute device/delivery system performance and procedure. The following information will be collected during the procedure.

- Date of procedure
- Specifics of device type (such as size and model)

- Time of first vascular puncture (femoral) and time of vascular closure (skin-to-skin time)
- Introducer insertion and removal time
- Descriptive information on balloon valvuloplasty (e.g., size of balloon, number of balloon inflations)
- Any devices used and adjunctive procedures performed during implant procedure
- Heart rhythm after balloon valvuloplasty with rhythm strip should be recorded (12-lead ECG is not required).
- Valve catheter insertion and removal time
- Descriptive information on valve implantation procedure
- Adverse event (AE) assessment and associated treatment (including AE, serious adverse event [SAE], serious adverse device effect [SADE], unanticipated adverse device effect [UADE]/unanticipated serious adverse device effect [USADE], adverse device effect [ADE] and Clinical Events Committee [CEC] events; see Section 21).
- Device deficiencies assessment

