- 8) A final post-deployment aortogram of the ascending aorta (including rotational angiography of the valve frame, required only for Lotus) must be performed and forwarded to the Core Laboratory with the procedural cine-angiogram for analysis.
- 9) The Lotus Introducer is then removed.
- 10) The femoral access is then closed according to standard practice.

Labels from the devices used during the procedure (e.g., the Lotus Valve System/LOTUS Edge Valve System, Lotus Introducer) should be retained so that they can be included in the appropriate source documents and reported in the eCRFs.

During the procedure, designated center study personnel must capture necessary information on acute device/delivery system performance and procedure. The following information will be collected during the procedure.

- Date of procedure
- Device size (21 mm, 23 mm, 25 mm, 27 mm, or 29 mm) and model
- Time of first vascular puncture (femoral) and time of vascular closure (skin-to-skin time)
- Lotus Introducer insertion and removal time
- Descriptive information on balloon valvuloplasty (e.g., size of balloon, number of balloon inflations)
- Any devices used and adjunctive procedures performed during implant procedure
- Heart rhythm after balloon valvuloplasty with rhythm strip should be recorded (12-lead ECG is not required).
- Lotus Valve System or LOTUS Edge Valve System catheter insertion and removal time
- Descriptive information on Lotus Valve implantation procedure and information on valve repositioning or retrieval (if performed)
- Adverse event (AE) assessment and associated treatment (including AE, serious adverse event [SAE], serious adverse device effect [SADE], unanticipated adverse device effect [UADE]/unanticipated serious adverse device effect [USADE], adverse device effect [ADE] and Clinical Events Committee [CEC] events; see Section 21).
- Device deficiencies assessment (for the Lotus Valve System/LOTUS Edge Valve System)

**Note:** All Lotus Valve implantation procedures will be performed with the support/presence of trained BSC personnel.

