**Table 21.3-1: Investigator Reporting Requirements**

Event Classification	Communication Method	Communication Timeline
Unanticipated Adverse Device Effect / Unanticipated Serious Adverse Device Effect (UADE/USADE)	Complete adverse event (AE) electronic case report form (eCRF) page with all available new and updated information	
 
Within 1 business day of first becoming aware of the event
 
Beginning from time of enrollment for all subjects
 
Terminating at the end of the study
 

	Provide copies of all relevant source documents requested by BSC	
 
As soon as possible after reporting the event
 

Serious Adverse Event (SAE) including Serious Adverse Device Effects (SADE)	Complete AE eCRF page with all available new and updated information	
 
Within 2 business days of first becoming aware of the event or as per local/regional regulations.
 
Beginning from time of enrollment for all subjects
 
Reporting required through the end of the study
 

	Provide all relevant source documentation (unidentified) for reported event	
 
When documentation is available
 

Adverse Event (AE)	Complete AE eCRF page	
 
As soon as possible before the next planned monitoring visit
 
Beginning from time of enrollment
 

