## **22. Committees**

### **22.1. Safety Monitoring Process**

To promote early detection of safety issues, the Clinical Events Committee (CEC) and Data Monitoring Committee (DMC; see below) will provide evaluations of safety events. Success of this program requires dynamic collection of unmonitored data as soon as the event is reported. This is expedited through the Sponsor or designee, which is responsible for coordinating the collection of information for the subject dossier from the centers and core laboratories. During regularly scheduled monitoring visits, clinical research monitors will support the dynamic reporting process through their review of source document information.

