#### **22.1.1. Clinical Events Committee**

A CEC will be used in this study. A CEC is an independent group of individuals with pertinent expertise, including cardiovascular interventional therapy, cardiovascular surgery, and neurology, which reviews and adjudicates important endpoints and relevant adverse events reported by study investigators. The CEC will review a safety event dossier, which may include copies of subject source documents provided by study sites, and adjudicate study endpoint related clinical events. The responsibilities, qualifications, membership, and committee procedures of the CEC are outlined in the CEC charter.

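### The protocol requires the Clinical Events Committee to be independent but not masked to the valve, which leaves the judgment calls in the primary safety endpoint open to drift by arm

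*Combined protocol and SAP*

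**What the plan says.** Section 22.1.1 describes the committee in terms of independence and expertise: "A CEC is an independent group of individuals with pertinent expertise". The Synopsis, under Additional Measurements, uses the same adjective, "Safety endpoints adjudicated by an independent Clinical Events Committee (CEC"), as does Section 7.2, and Section 21.1 lists the events to be adjudicated. Those events cover every component of the primary safety endpoint, together with death and stroke in the primary effectiveness endpoint. Paravalvular regurgitation is read by the echocardiography core laboratory.

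On materials, Section 22.1.1 says "The CEC will review a safety event dossier, which may include copies of subject source documents provided by study sites". Section 22.1 makes the sponsor or its designee responsible for "coordinating the collection of information for the subject dossier from the centers and core laboratories".

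Source documents in both arms are set up to carry the device name. For the control arm (Section 11.7.1): "Labels from devices used during the procedure (e.g., CoreValve, Introducer, etc.) should be retained so that they can be included in the appropriate source" documents. For the test arm (Section 11.7.2.2): "Labels from the devices used during the procedure (e.g., the Lotus Valve System/LOTUS Edge Valve System, Lotus Introducer) should be retained", for the same purpose. Table 21.3-1 tells sites to "Provide all relevant source documentation (unidentified) for reported event". It does not define the bracketed word and does not mention the device.

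Section 12.2.2, on control of bias, relies on independent core laboratories and says nothing about masking. Section 22.1.1 leaves the rest to another document: "committee procedures of the CEC are outlined in the CEC charter".

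**The concern.** Operators necessarily know which valve they implant, so the main protection against differential classification lies at adjudication. Independence removes a conflict of interest. It does not remove expectation when the reviewer can see which valve was used.

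Some definitions in Table 26.2-1 leave room for judgment. Whether bleeding is overt, and whether an access injury led to major bleeding, ischemia or neurological impairment, decides whether an event counts. A stroke diagnosis requires that no other cause is readily identifiable.

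The primary safety test is one-sided non-inferiority with a 10.5-point margin. A small net tendency to grade Lotus events more leniently would move the observed difference toward a claim of non-inferiority. The sensitivity analyses in Section 12.1.1.3 address missing data and events before the procedure, not differential adjudication.

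**Working it through.** **Inputs.** Section 12.1.1.2: 608 and 304 subjects, 5% attrition, 40% expected in each arm, margin 10.5 points, one-sided alpha 0.025. Table 4.1-4: 30-day major bleeding of 21.5% (53/247) in the REPRISE II full cohort. The documents give no figure for adjudication drift, so every shift below is an assumption.

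**Formula.** Farrington-Manning normal approximation: z = [Δ − (p₁ − p₂) − 1.960·s₀]/s₁. Here s₁ is the standard error at the assumed rates, and s₀ is the standard error at the restricted maximum-likelihood rates with the difference held at Δ. The chance of declaring non-inferiority is Φ(z).

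**The plan's own figure.**
- Evaluable: 608 × 0.95 = 577.6 and 304 × 0.95 = 288.8.
- At 40% versus 40% the restricted rates are 43.7% and 33.2%, so s₀ = 0.03456 and s₁ = 0.03531.
- z = (0.105 − 1.960 × 0.03456)/0.03531 = 1.055, which gives 85.4%. The plan states about 85%, so it reproduces.

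**Choosing a range of shifts.**
- If 5% or 10% of Lotus major bleeds were downgraded: 21.5 × 0.05 = 1.075 points; 21.5 × 0.10 = 2.15 points.
- A downgraded bleed changes the composite only if the subject had no other component event. The six REPRISE II 30-day components sum to 4.4 + 7.1 + 7.3 + 21.5 + 2.9 + 5.4 = 48.6%, against a planned composite of 40%. That suggests overlap but does not measure it.
- If half of the downgraded bleeds were the only component event (assumption), the shifts halve to 0.54 and 1.08 points.

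**Effect on type I error.** Set the true Lotus rate at the margin (50.5% versus 40%) and lower the adjudicated Lotus rate by b. Then z = (b − 1.960·s₀)/s₁.

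| Shift b (points) | Lotus subjects reclassified | s₀ | s₁ | z | Type I error |
|---|---|---|---|---|---|
| 0 | 0 | 0.03555 | 0.03555 | −1.960 | 2.5% |
| 0.5 | 2.9 | 0.03552 | 0.03555 | −1.818 | 3.5% |
| 1.075 | 6.2 | 0.03548 | 0.03555 | −1.654 | 4.9% |
| 2.15 | 12.4 | 0.03540 | 0.03554 | −1.347 | 8.9% |

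The last row is an upper case: 10% of Lotus major bleeds are downgraded, all in one direction, and each was the subject's only component event.

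**Drift against Lotus.** With true rates equal at 40%, power falls from 85.4% to 77.8% at 1 point and to 68.2% at 2 points.

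**Effectiveness endpoint.** With 546 and 273 evaluable, 32% in each arm and a 9.5-point margin, power is 80.1% against a stated 80%. At the margin, a 1-point shift would give a type I error of about 4.7%. Only stroke can shift through the committee, and REPRISE II disabling stroke at 1 year was 3.6% (Table 4.1-4). A 1-point shift would therefore need 1/3.6 = 28% of disabling strokes to be reclassified, so a shift of that size is much less plausible here.

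**The case against.** The strongest reply is that committee procedures sit in the charter, and masking is a committee procedure. This stands. A reader might infer that the committee is in fact unmasked, but the documents are silent on that.

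A reader might also infer that the committee routinely works from records naming the valve. Section 22.1.1 says only that the dossier may include site source documents, and the label instructions do not say that labels enter the event dossier. What remains is that the protocol permits this route and states no step that closes it.

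The CT substudy keeps valve readings from local investigators (Sections 7.2 and 11.10.1). It is tempting to conclude that masking was considered there and passed over for the committee. That substudy has a single arm, so its rule is not treatment masking and supports no such conclusion.

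Several definitions are more rule-bound than they first appear. Major bleeding has hemoglobin and transfusion thresholds, kidney injury has creatinine and urine-output thresholds, and all-cause death needs no grading. Non-focal encephalopathy is not reported as stroke without unequivocal imaging evidence, so it is not a good example of an open call. The disabling grade follows the 90-day modified Rankin score. These points narrow the exposure but do not remove it.

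Finally, many bleeding and vascular events are periprocedural, and their narratives will describe device-specific steps. Masking will therefore be partial.

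**Conclusion.** The gap is real and modest. The documents require independence and do not require masking of the committee that classifies every safety component. The exposure lies mainly in the bleeding, vascular and stroke calls of the primary safety endpoint, and through stroke alone in the effectiveness endpoint.

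A reasonable sensitivity range for the safety type I error is 3.5-4.9% instead of 2.5%, with 8.9% as an upper case. A reader might take these as estimates of bias. They are not: they assume that all drift favors Lotus, that CoreValve calls are unaffected and that the true difference sits at the margin. The conclusion also depends on the charter, which could settle the point.

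**What to change.** State in Section 22.1.1, and make the charter consistent, that the following applies to stroke, bleeding, acute kidney injury and vascular complications in the randomized cohort:

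- When the dossier is assembled, the sponsor or designee removes valve brand, model, size, introducer and treatment assignment where feasible.
- The committee votes without that information.
- Events that cannot be masked are listed, such as malpositioning, a second valve placed inside the first, valve thrombosis and repeat valve procedures.

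If the charter already requires this, a citation in Section 22.1.1 is enough.

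The cost is a paragraph in each document, redaction effort at a step the sponsor or designee already coordinates, and slightly slower dossiers. It needs no extra reviewers or subjects. Some procedure narratives will still reveal the device, so the protection is incomplete.
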